4.4.3. Exploratory Virology Endpoints

The virology analyses will be based on the "Safety" population.

Missing data for the endpoints in this section will be ignored without any imputation.

4.4.3.1. HBV Genotype

HBV Genotype will be collected in the eCRF as well as identified by HBV Sequence. HBV Genotype from both data sources will be listed and the listing will include the final reported genotype.

For subjects with genotype both collected in the eCRF and determined by HBV Sequence the final reported genotype will be determined as follows:

For participants on stable nucleos(t)ide treatment:

• Genotype reported in the eCRF will take precedence

For participants currently not on nucleos(t)ide treatment:

- If the if the sequence genotype was derived from DNA, the HBV Sequence genotype will take precedence.
- If the if the sequence genotype was derived from RNA (i.e. rather than DNA due to low DNA levels hence RNA sequencing was employed), the genotype reported in the eCRF will take precedence similar to the participants on stable nucleos(t)ide.

Data from the Week 1 Day 1 visit will be used to determine HBV genotype by HBV DNA or RNA sequencing. However, as HBV genotype should not change over time, if a participant missed the Week 1 Day 1 visit, HBV genotype can be determined from a later sample if available.

The number of participants with each final reported genotype will be presented by arm and overall.

Baseline log HBsAg, change from baseline in log HBsAg at End of GSK836 Treatment visit (Week 12 / Week 24) and Off GSK836 Treatment Week 24 visit (Week 36 / Week 48), number of subjects achieving HBsAg < LLOQ at any time up to End of GSK836 Treatment visit (Week 12 / Week 24) or Off GSK836 Treatment Week 24 visit (Week 36 / Week 48), and mean time to achieving HBsAg < LLOQ will be presented for each arm separately. Results will be summarized by baseline final reported genotype.

For participants currently not on nucleos(t)ide treatment only, baseline log HBV DNA, change from baseline in log HBV DNA at End of GSK836 Treatment visit (Week 12 /

Week 24) and Off GSK836 Treatment Week 24 visit (Week 36 / Week 48), number of subjects achieving HBV DNA < LLOQ at any time up to End of GSK836 Treatment visit (Week 12 / Week 24) and Off GSK836 Treatment Week 24 visit (Week 36 / Week 48), and mean time to achieving HBV DNA < LLOQ will be presented for each arm separately. Results will be summarized by baseline final reported genotype.

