- Achieving HBsAg <LLOQ and HBV DNA <LLOQ at the end of treatment analysis window. Data will be presented overall and by baseline stratification factors (HBsAg <3 log IU/mL and Negative HBeAg; BsAg >3 log IU/mL and Negative HBeAg; HBsAg <3 log IU/mL and Positive HBeAg; HBsAg >3 log IU/mL and Positive HBeAg; HBsAg <3 log IU/mL and All HBeAg; All HBsAg and Negative HBeAg; HBsAg <3 log IU/mL and All HBeAg; All HBsAg and Positive HBeAg)
- Categorical changes from baseline in HBsAg (e.g., <0.5, ≥0.5, ≥1, ≥1.5, ≥3 log₁₀ IU/mL) and in HBV DNA (e.g., <1, ≥1, ≥2, ≥3 log IU/mL). Change from baseline will be presented at each visit and for the following time periods: up to and including Week 6, Up to and including Week 12, Up to and including Week 24, Up to and including off-treatment Week 24. Data will be presented overall and by baseline stratification factors (HBsAg <3 log IU/mL and Negative HBeAg; BsAg >3 log IU/mL and Negative HBeAg; HBsAg >3 log IU/mL and Positive HBeAg; HBsAg >3 log IU/mL and All HBeAg; All HBsAg and Negative HBeAg; HBsAg <3 log IU/mL and All HBeAg; All HBsAg and Positive HBeAg)
- ALT normalization (ALT \leq ULN) over time in absence of rescue medication in participants with baseline ALT \rightarrow ULN
- HBe antibody (anti-HBeAg) levels in HBeAg Positive patients
- HBs antibody (anti-HBsAg) levels (HBs Antibody >=11.5 IU/L is HBs antibody positive and HBs Antibody <11.5 IU/L is HBs antibody negative)
- **Population summary:** proportion of participants in each category for each treatment arm.

2) Continuous Variables:

- Actual values and change from baseline over time of HBsAg and HBV DNA
- Actual values and change from baseline of HBeAg levels
- HBs antibody (anti-HBsAg) levels
- **Population summary**: mean values and mean changes from baseline for each variable in each treatment arm.

3) Time to Event Variable:

- Time to ALT normalization in absence of rescue medication in participants with baseline ALT>ULN.
- **Population summary**: Turnbull's estimator for the non-parametric estimation of time to ALT normalization in each treatment arm.

ALT normalization is defined in subjects with ALT>ULN at baseline as a return to ≤ULN (ULN = 40 for males and 33 in females). Time to ALT normalization is defined as time from baseline to the first follow-up where subject's ALT has returned to normal.

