4.4.3.2. HBV Sequences

Baseline and treatment emergent nucleotide changes both within HBV binding site and outside of the HBV binding site will be summarized by number of subjects for each arm and overall and data will be listed.

The following steps can be followed to identify nucleotide changes within the HBV binding site:

- 1. Identify nucleotide sequence records
- 2. Identify the 20ntd binding site of HBV at the following locations: 1581 1600
- 3. If the allelic frequency meets the threshold for a mutation flag as a mutation

Participants who have data in the PF dataset but have no binding site mutations will be considered Wild Type for the binding site.

Mutations that are reported for >1 genetic location of interest will only be reported once.

Unless otherwise specified, a >=5% threshold of allelic frequency will be used to report a mutation vs wild type and only observations meeting this threshold will be included in summary tables. However, mutations >=1% and <5% will be reported in the Listing of Mutations in the Binding Site in Participants with Mutation at Any Time for full transparency. Mutations will be reported as "variant" if >=15% and "minority species", >=5% and <15%.

Development of a mutation during therapy (i.e. treatment emergent) will be defined as a substitution present at <5% at baseline but detected at >=5% post baseline.

Baseline log HBsAg, change from baseline in log HbsAg at End of GSK836 Treatment visit (Week 12 / Week 24) and Off GSK836 Treatment Week 24 visit (Week 36 / Week 48), number of subjects achieving HbsAg < LLOQ at any time up to End of GSK836 Treatment visit (Week 12 / Week 24) and Off GSK836 Treatment Week 24 visit (Week 36 / Week 48), and mean time to achieving HbsAg < LLOQ will be presented for each arm separately. Results will be summarized by baseline binding site polymorphism.

For participants currently not on nucleos(t)ide treatment only, baseline log HBV DNA, change from baseline in log HBV DNA at End of GSK836 Treatment visit (Week 12 / Week 24) and Off GSK836 Treatment Week 24 visit (Week 36 / Week 48), number of subjects achieving HBV DNA < LLOQ at any time up to End of GSK836 Treatment visit (Week 12 / Week 24) and Off GSK836 Treatment Week 24 visit (Week 36 / Week 48), and mean time to achieving HBV DNA < LLOQ will be presented for each arm separately. Results will be summarized by baseline binding site polymorphism.

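### The exploratory mean time to HBsAg or HBV DNA <LLOQ has no rule for participants who never reach it, so a group with extra, later responses can look slower

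*SAP*

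**What the plan says.** SAP 4.4.3.1 (HBV Genotype) plans for HBsAg that "mean time to achieving HBsAg < LLOQ will be presented for each arm separately" and adds that "Results will be summarized by baseline final reported genotype". For the population not on nucleos(t)ide therapy it also plans that "mean time to achieving HBV DNA < LLOQ will be presented for each arm separately". SAP 4.4.3.2 (HBV Sequences) repeats both summaries; there "mean time to achieving HbsAg < LLOQ will be presented for each arm separately" and "Results will be summarized by baseline binding site polymorphism".

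One rule in SAP 4.4.3 covers the whole section: "Missing data for the endpoints in this section will be ignored without any imputation". Nothing there says how a participant who never reaches <LLOQ enters the mean, when the clock starts, or over what period the event is sought.

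The sentence that plans the HBsAg mean also plans a count, the "number of subjects achieving HBsAg < LLOQ at any time up to End of GSK836 Treatment visit (Week 12 / Week 24"), with a second count up to 24 weeks off treatment (Week 36 or Week 48).

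Elsewhere the documents treat such variables as event times. Protocol 8.6 lists HBsAg seroclearance and HBV DNA below LLOQ among its time-to-event parameters. For time to ALT normalization, SAP 4.3.1.1 uses Turnbull's "estimator for the non-parametric estimation of time to ALT normalization in each treatment arm". It censors at the last visit with an ALT value and has a separate rule for participants who take rescue medication.

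**The concern.** A participant who never falls below LLOQ has no time to achieving it. With no censoring rule and missing values dropped, the obvious way to program the mean is to average those who got there. That conditions on the outcome: non-achievers and dropouts contribute nothing, and each response later than the current mean pushes the mean up. A longer course of treatment, or a more responsive genotype, could gain responses and appear slower for it.

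The means will be read across genotype and polymorphism groups within an arm, and probably across arms. Arms 1 and 2 receive active drug for 24 weeks and Arm 3 for 12, so later responses in some arms are plausible. Arm 4 has 12 placebo weeks first. If its clock starts at the first study dose, those 12 weeks are added to the time of every participant who responds to active drug.

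**Working it through.** The SAP gives no expected value for this mean, so there is no figure of its own to reproduce. Every response time below is assumed.

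**When the mean misleads.** Let a group have n1 achievers with mean time m1, and let a second group have the same achievers plus n2 more with mean m2. The second group's achiever-only mean is (n1·m1 + n2·m2)/(n1 + n2). It exceeds m1 exactly when m2 > m1. Cumulative response in the second group is never lower. Only the ratio n1:n2 matters, so the same holds in small genotype groups.

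**Illustration in percentages.** Group A: 20% reach <LLOQ evenly over Weeks 4–12, mean 8.0 weeks. Group B: the same 20% plus 15% evenly over Weeks 12–24, mean 18 weeks.

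- B's mean = (20 × 8 + 15 × 18)/35 = 430/35 = 12.3 weeks.
- B looks 12.3 − 8.0 = 4.3 weeks slower and ends 15 percentage points higher.

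**Illustration in counts.** The arm size of 66 is from SAP Section 5. The counts 12/66 (18%) and 18/66 (27%) are rows of SAP Table 10. As a check on those rows, the Beta(0.5, 0.5) intervals recompute to 9.8–28.0% and 17.3–38.3%, against 10–28% and 17–38% in the table. They are sustained-response counts, borrowed only as plausible sizes; the SAP assumes no rate for reaching <LLOQ at any time.

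- A: 12 achievers at Weeks 6 (two), 8 (three), 10 (three) and 12 (four). Sum 114, mean 114/12 = 9.5 weeks.
- B: the same 12 plus six at Weeks 18, 20, 20, 22, 22 and 24. Sum 114 + 126 = 240, mean 240/18 = 13.3 weeks.

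| Summary | A | B |
|---|---|---|
| Mean among achievers (weeks) | 9.5 | 13.3 |
| Cumulative response, Week 16 | 18.2% | 18.2% |
| Cumulative response, Week 20 | 18.2% | 22.7% |
| Cumulative response, Week 24 | 18.2% | 27.3% |
| Restricted mean over all 66, 24-week horizon | (114 + 54 × 24)/66 = 21.36 | (240 + 48 × 24)/66 = 21.09 |
| Restricted mean over all 66, 48-week horizon | (114 + 54 × 48)/66 = 41.0 | (240 + 48 × 48)/66 = 38.5 |

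Once everyone is counted, B is no longer slower on any row.

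**Sensitivity to timing.** With all six extra responses at Week 16, 20 or 24, B's achiever-only mean is 11.7, 13.0 or 14.3 weeks. At Week 8 it is 9.0, below A's 9.5, and the distortion disappears. With all six at Week 24, the 24-week restricted means tie at 21.36.

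**Simulation.** There were 20,000 runs with 66 per group: A with 18.2% responding over Weeks 4–12, B the same plus 9.1% over Weeks 14–24. B's achiever-only mean was 3.7 weeks longer on average, and B looked slower in 99% of runs. B's 24-week restricted mean was 0.44 weeks shorter on average, and shorter in 66% of runs, because that difference is small against sampling noise.

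**The case against.** A reader might infer that the SAP defines the mean in achievers only. It does not. Its missing-data sentence is about missing values, and a participant observed throughout without reaching <LLOQ is a non-event rather than plainly missing. The SAP sends output detail to a programming specification that is not among the documents. What is certain is that the denominator is unspecified; achievers-only is the natural reading, not a stated one.

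A reader might also infer that the virology objective is misled. That goes too far. The achiever count sits beside the mean, so in the first illustration 20% and 35% would appear next to 8.0 and 12.3 weeks. SAP 4.4.3.2 cross-tabulates baseline mutations against end-of-treatment response and SVR. Table 7 in SAP 4.6.1 gives SVR by genotype and, for those not on nucleos(t)ides, by binding-site substitution. No estimand or decision rule uses the mean. All of this stands and limits the consequence. However, a count up to one or two landmarks does not show when responses accrued, and it does not repair the mean.

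Using Turnbull for a secondary variable and something lighter for an exploratory one is a choice, not a contradiction. Nor do the documents show that most participants fail to reach HBV DNA <LLOQ in the population not on nucleos(t)ides. Subgroup curves would also be sparse: 20% of 66 is about 13 achievers per arm before any split by genotype. That affects how the fix is applied, not whether the mean is sound.

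**Conclusion.** The point holds as a minor one. As specified, the mean most naturally averages achievers only, and it can rank a group with more, later responses as slower: 12.3 against 8.0 weeks, or 13.3 against 9.5, in the illustrations. This rests on the achievers-only reading and on extra responses arriving later than the other group's mean; earlier ones remove or reverse the effect. The size in this trial is unknown because all response times are assumed. The primary and secondary analyses and regimen selection are untouched. What is at risk is a descriptive time column that could be read as speed of response.

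**What to change.** In SAP 4.4.3.1 and 4.4.3.2, replace the mean with the Turnbull (or Kaplan-Meier) cumulative proportion reaching <LLOQ at fixed weeks. Turnbull fits better because both markers are seen only at visits, the reason Protocol Appendix 9 gives for choosing it for ALT. State four things:

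- **Origin:** first active GSK3228836 dose, with a line on Arm 4 participants who leave, or reach <LLOQ, before it.
- **Window:** common to the arms compared. With all four arms, planned follow-up allows at most 48 − 12 = 36 weeks, set by Arm 4.
- **Censoring:** non-achievers at their last non-missing assessment.
- **Rescue, for HBV DNA:** as in the existing ALT rule, so no achievement is credited after rescue.

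Where a genotype or polymorphism group has too few events for a curve, show the number and percentage achieving by the fixed weeks. Label any mean that is kept *among achievers, n=* and do not compare groups on it.

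The cost is SAP wording and a little programming, since a Turnbull analysis is already planned for ALT. No new data or visits are needed. Estimates in small subgroups will be imprecise.

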4.4.3.2. HBV Sequences

Baseline and treatment emergent nucleotide changes both within HBV binding site and outside of the HBV binding site will be summarized by number of subjects for each arm and overall and data will be listed.

The following steps can be followed to identify nucleotide changes within the HBV binding site:

- 1. Identify nucleotide sequence records
- 2. Identify the 20ntd binding site of HBV at the following locations: 1581 1600
- 3. If the allelic frequency meets the threshold for a mutation flag as a mutation

Participants who have data in the PF dataset but have no binding site mutations will be considered Wild Type for the binding site.

Mutations that are reported for >1 genetic location of interest will only be reported once.

Unless otherwise specified, a >=5% threshold of allelic frequency will be used to report a mutation vs wild type and only observations meeting this threshold will be included in summary tables. However, mutations >=1% and <5% will be reported in the Listing of Mutations in the Binding Site in Participants with Mutation at Any Time for full transparency. Mutations will be reported as "variant" if >=15% and "minority species", >=5% and <15%.

Development of a mutation during therapy (i.e. treatment emergent) will be defined as a substitution present at <5% at baseline but detected at >=5% post baseline.

Baseline log HBsAg, change from baseline in log HbsAg at End of GSK836 Treatment visit (Week 12 / Week 24) and Off GSK836 Treatment Week 24 visit (Week 36 / Week 48), number of subjects achieving HbsAg < LLOQ at any time up to End of GSK836 Treatment visit (Week 12 / Week 24) and Off GSK836 Treatment Week 24 visit (Week 36 / Week 48), and mean time to achieving HbsAg < LLOQ will be presented for each arm separately. Results will be summarized by baseline binding site polymorphism.

For participants currently not on nucleos(t)ide treatment only, baseline log HBV DNA, change from baseline in log HBV DNA at End of GSK836 Treatment visit (Week 12 / Week 24) and Off GSK836 Treatment Week 24 visit (Week 36 / Week 48), number of subjects achieving HBV DNA < LLOQ at any time up to End of GSK836 Treatment visit (Week 12 / Week 24) and Off GSK836 Treatment Week 24 visit (Week 36 / Week 48), and mean time to achieving HBV DNA < LLOQ will be presented for each arm separately. Results will be summarized by baseline binding site polymorphism.

For all observed mutations in the binding site at baseline and for frequently (e.g. in >=5% subjects) observed mutations outside of the binding site at baseline, a 2x2 contingency table of mutation (present / absent) vs. response at end of GSK836 treatment (Yes / No) and response at Off GSK836 Treatment Week 24 (Yes / No) will be presented. Response at end of GSK836 treatment will be defined as HBV DNA < LLOQ, HBsAg < LLOQ and no rescue medication at the end of treatment analysis window. Response at 24 weeks off GSK836 treatment will be defined as SVR. The table will be repeated using a >=1% threshold of allelic frequency, for all mutations in the binding site only.

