Virology: To assess the effect of genotype/phenotype and presence of baseline polymorphisms within the GSK3228836 binding site to assess the effect on treatment response. To assess the emergence of mutations within the GSK binding site, and elsewhere in the hepatitis B genome, during and after treatment.	Sequencing of the viral HBV DNA and/or HBV RNA prior to treatment, during treatment and post treatment visits
Immunology: To assess the effect of 12 weeks, 12 weeks + 12 weeks step-down or 24 weeks treatment with GSK3228836 on immunological biomarkers. To describe the relationship(s) between virology biomarkers, including but not limited to HBsAg, and immunological biomarkers.	 Laboratory measurements of and correlation between the following Virological biomarkers, as determined by (but not limited to) specific viral parameters (HBeAg, HBV DNA, HBV RNA, HBcrAg). Soluble immunological biomarkers, as determined by (but not limited to) levels of circulating cytokines and chemokines. Markers of immune cell function, as measured by (but not limited to) relative frequencies of immune cell subsets among PBMCs, activation status as determined by phenotyping and gene expression patterns, and functional assays including HBV-specific cytokine and/or antibody production
Patient Reported Outcomes: To assess changes from baseline in patient reported outcomes following 12 weeks, 12 weeks + 12 weeks stepdown, and 24 weeks of treatment with GSK3228836.	Change from baseline of HBQOL and EQ-5D.

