8.9. HBV Resistance Monitoring

Samples collected for viral genotyping and phenotyping may be used for HBV resistance mutation analysis. Viral DNA and/or viral RNA will be extracted from participant samples and the viral genome will be DNA sequenced to determine whether mutations have occurred in the GSK3228836 binding region or elsewhere in the genome (and if applicable, whether any known nucleos(t)ide resistance mutations are present in the polymerase coding region).

Resistance monitoring will be conducted on all baseline isolates to identify pre-existing substitutions. Sequencing of the viral RNA will be attempted in participants receiving stable NA therapy and having DNA <LLOQ. Additional resistance monitoring will be conducted and will include, but not limited to, the analysis of isolates from participants experiencing virological failure during or post treatment as defined below. Confirmation of resistance should be done within 1 week after results are received.

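### The treatment-emergent rule in SAP 4.4.3.2 cannot show enrichment of a variant already at 5% or more, counts any crossing of 5%, and lets an unread binding site default to wild type

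*SAP*

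**What the plan says.** The exploratory virology objective in Protocol Section 3 includes this aim: "To assess the emergence of mutations within the GSK binding site, and elsewhere in the hepatitis B genome, during and after treatment". SAP 4.4.3.2 sets the rules that serve it.

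- **Calling a mutation.** Unless otherwise specified, "a >=5% threshold of allelic frequency will be used to report a mutation vs wild type". A mutation at 15% or more is labelled a variant, and one from 5% to below 15% a minority species.
- **Emergence.** A treatment-emergent mutation "will be defined as a substitution present at <5% at baseline but detected at >=5% post baseline". No minimum rise, confirmation or persistence is required.
- **Displays.** "Baseline and treatment emergent nucleotide changes both within HBV binding site and outside of the HBV binding site will be summarized by number of subjects", by arm and overall, with the data listed. Below the main threshold, "mutations >=1% and <5% will be reported in the Listing of Mutations in the Binding Site in Participants with Mutation at Any Time".
- **Wild type.** "Participants who have data in the PF dataset but have no binding site mutations will be considered Wild Type for the binding site".
- **Response tables.** Each binding-site mutation observed at baseline is cross-tabulated, as present or absent, against end-of-treatment response and SVR. For the binding site this is repeated at a 1% threshold.

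SAP 4.6.1, Table 7, adds an SVR subgroup for baseline binding-site substitution. It covers only participants not on nucleos(t)ides (NA) and has two levels, present and absent. Baseline genotype, in the same table, also has an unknown level.

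**The concern.** A binding-site variant can come to dominate in two ways: it arises during treatment, or treatment selects one that was already there. The emergent rule captures the first and excludes the second whenever the starting frequency is 5% or more. Protocol 6.5.2 states that the barrier to resistance is unknown, so neither route can be set aside in advance.

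The same rule has no margin at its upper side. One post-baseline sample just over 5% is enough, however small the change, and more samples mean more chances to cross.

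The wild-type default raises a different question. It works per participant and requires some record in the sequencing dataset. It does not require that the 20-nucleotide site was read at baseline. A participant whose records cover another region or only a later visit could enter the absent column of the response tables without evidence that the site was unmutated.

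At stake are the by-arm summary of on-treatment change and the comparison of response between participants with and without a baseline binding-site mutation.

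**Working it through.** The plan states no error rate or expected count for this rule, so there is no figure to reproduce. The check applies the written rule to test cases and then to a variant that does not change.

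**1. Test cases** (rule and bands from SAP 4.4.3.2)

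| Baseline | Highest post-baseline | Emergent? | Band movement |
|---|---|---|---|
| 6% | 95% | No | minority species to variant |
| 14.9% | 99% | No | minority species to variant |
| 16% | 95% | No | none |
| 4.9% | 5.1% | Yes | below threshold to minority species |
| 0% | 6% | Yes | below threshold to minority species |

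This part follows from the text and needs no assumption.

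**2. Unchanged variant near 5%**

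Inputs:
- Post-baseline sequencing samples, from Protocol Tables 2 to 4: on-treatment Weeks 4, 8, 12, 16, 20 and 24 (6), plus off-treatment Weeks 1, 4, 12, 20 and 24 (11 in all).
- Read depth: not in the documents. Assumed 200 to 10,000, with binomial error only and independent samples.

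Let f be the constant true frequency, q the probability that one sample reads 5% or more, and k the number of post-baseline samples. Then

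P(called emergent) = (1 − q) × [1 − (1 − q)^k].

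Example: f = 4.5%, depth 1,000, q = 0.2424, k = 6 gives 0.7576 × (1 − 0.7576^6) = 0.7576 × (1 − 0.189) = 0.614.

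| True f | Depth | q | k = 1 | k = 6 | k = 11 |
|---|---|---|---|---|---|
| 3.0% | 200 | 0.0808 | 7.4% | 36.5% | 55.5% |
| 4.0% | 200 | 0.2808 | 20.2% | 62.0% | 70.0% |
| 3.0% | 1,000 | 0.0004 | 0.0% | 0.3% | 0.5% |
| 4.0% | 1,000 | 0.0663 | 6.2% | 31.5% | 49.5% |
| 4.5% | 1,000 | 0.2424 | 18.4% | 61.4% | 72.2% |
| 4.0% | 5,000 | 0.0003 | 0.0% | 0.2% | 0.3% |
| 4.5% | 5,000 | 0.0491 | 4.7% | 24.8% | 40.4% |
| 4.5% | 10,000 | 0.0093 | 0.9% | 5.4% | 9.6% |

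The effect sits in a band around 5% that narrows as depth rises. Noise beyond binomial widens it: with beta-binomial correlation 0.001 (assumed) at depth 1,000, the 3.0% variant goes from 0.3% and 0.5% to 6.2% and 11.0% for k = 6 and 11.

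A cut at 15% is not exposed in this way. For f = 4.5% the binomial SD is √(0.045 × 0.955 / 1,000) = 0.66 points, so 15% lies (15 − 4.5) / 0.66 ≈ 16 SDs away. At depth 200 the SD is 1.47 points and the distance about 7 SDs.

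**3. Wild-type default**

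If a share u of classified participants has sequence records but no baseline read of the site, and none of them has a recorded mutation, a true prevalence m is reported as m × (1 − u). Purely as illustration, m = 20% reads as 19% for u = 5% and 14% for u = 30%. The documents give no value for u.

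They do show where u is likely to be larger. Under Protocol 5.1, participants on NA enter with HBV DNA below 90 IU/mL, and Protocol 8.9 says "Sequencing of the viral RNA will be attempted in participants receiving stable NA therapy and having DNA <LLOQ". Participants not on NA enter above 2,000 IU/mL.

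**The case against.** Variants at 5% or more at baseline are not ignored. They are in the baseline summary, the listings and the mutation-by-response tables, and the band labels apply to them. This stands: what is missing is a summary of change. But the baseline row cannot separate a variant that stayed at 6% from one that took over, and a listing is not a summary by arm.

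The noise figures depend on an assumed depth, are conditional on a variant just under 5%, and may assume too many reads. Protocol 8.9 says samples may be used for resistance analysis and does not promise 11 reads per participant. All of this stands. Even one post-baseline sample can produce a false call, but its effect on any reported count cannot be stated.

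Protocol 8.9 also asks that resistance be confirmed within a week of results, and 8.9.1 and 8.9.2 require two sequential results. The latter criteria select isolates for analysis, and the SAP's emergent definition refers to no confirmation.

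A reader might infer that participants without sequence data are counted as wild type. They are not: the default applies only to those with records, and SAP 4.4.3 drops missing virology data rather than imputing them. A reader might also infer that an unread baseline mutation becomes emergent when seen later. SAP 4.1.2 leaves a missing baseline missing and derives nothing from it, so that does not follow. The narrower gap remains. How failed reads are stored is not stated, and the default assigns a category instead of leaving the result missing. SAP 4.4.3.1 provides for a missed Day 1 sample for genotype; 4.4.3.2 has no counterpart for mutations.

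**Conclusion.** The point holds in three limited parts.

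1. **Enrichment.** Certain from the text. A rise from any baseline at or above 5% can never count as treatment emergent, and the SAP specifies no other summary of that change.
2. **Crossing of 5%.** Certain in logic, unknown in size. It matters for variants close to 5% and is negligible further away at high depth.
3. **Wild-type default.** A real gap in wording. It affects participants who have sequence records but no baseline read of the site. Their number is not known. On-NA participants are the likelier group, and they are outside the Table 7 subgroup but inside the response tables.

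It would be tempting to conclude that resistance selection is misreported. The documents do not support that: the listings would let a reader see selection participant by participant, and no primary or regimen-selection result uses these counts. The supported conclusion is that the summary counts can omit enrichment and include trivial crossings, and that the absent column can include unread sites. As the objective is exploratory, the priority is low to moderate.

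**What to change.** Amend SAP 4.4.3.2 and the related tables as follows.

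- Keep the emergent row, split by the SAP's own bands: below 5% to 5–<15%, flagged as seen in one sample or in more than one; and below 5% to 15% or more.
- Add a row for enrichment on treatment among variants at 5% or more at baseline, with a prespecified minimum rise. A minimum rise is better than a band change, which would miss 16% to 95% and count 14.9% to 15.1%. Set it from the assay's reproducibility. Ten percentage points, the width of the minority-species band (15 − 5), is one option.
- Assign wild type at a visit only if positions 1581 to 1600 were read at that visit; otherwise record not evaluable. Carry that level into the mutation-by-response tables and the Table 7 subgroup.
- Use participants with an evaluable baseline as the denominator, and paired baseline and post-baseline reads for emergence and enrichment.
- State the read depth, or the minimum coverage for a valid call, so that readers can judge the 5% threshold.

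The cost is SAP wording, one or two extra table rows, one extra category and slightly smaller denominators. No new samples are needed.
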